# Specific Aim 2 will describe the pharmacokinetics of anakinra and test the hypothesis that anakinra will decrease systemic and coronary artery inflammation associated with acute KD.

Blood will be tested pre-drug administration, 48 hours after initiation of therapy and at 2 weeks and 6 weeks for markers of inflammation and enumeration of dendritic cells and T cells. Echocardiographic assessment of CAA at these time points will be compared to historical controls matched for age, sex, illness day at diagnosis, and coronary artery status on initial echo.

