### 11B. Inclusion

#### 11B1. Inclusion for Phase I/IIa anakinra study

- Meets clinical criteria for KD according to American Heart Association guidelines (Table 4): Fever (T≥38°C or 100.4°C) ≥ 3 days and ≥ 2 clinical criteria with LAD or RCA z-score ≥ 2.5
- 2. Patient is at least 28 days old
- 3. Patient presents within the first 20 days after fever onset
- 4. Parent or legal guardian able and willing to provide informed consent
- 5. Able to be dosed between 20 mg (min amount on syringe) and 200 mg at 8 mg/kg/day

Dose escalation level*	Minimum subject weight to administer 20 mg	Maximum subject weight to administer 200 mg
8 mg/kg	2.5 kg	25 kg

\*This table includes only the 8 mg/kg dose level as enrollment in the 4 and 6 mg/kg cohorts has been completed as of the Nov 2016 revision.

\*As of the August 2017 revision, we have enrolled 2 subjects at 8mg/kg/day without any dose limiting toxicities.

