# 18. Measures of Activity

#### 18A. Measures of inflammation for Phase I/IIa anakinra study

Transcript abundance will be measured in whole blood by microarray. Levels of hsCRP,  $\alpha$ -1antitrypsin and fibrinogen, and the WBC and ESR will be measured in the hospital clinical laboratory. Levels of TNFaR1 and R2, IFNg, IL-1 RAP, IL-1R1 and R2, MMP9, caspase-1, IL-6R, IL-18RAP, IL-12, sIL-2R, TGFb and IL-10 will be measured by ELISA. Results of transcript abundance and measures of inflammation will be compared to database controls from the KD Research Center (>600 KD patients with available RNA and plasma samples in our biorepository) matched (1 case: 2 controls) by age (± 2 yrs. with lower limit of 2 yrs.), sex, and coronary artery Z-score.

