#### 19B. Statistical analysis of inflammatory studies

**19B1. Statistical analysis of inflammation studies for Phase I/IIa anakinra study** The objective of this matched case-control study is to determine the activity profile of anakinra in the treatment of KD subjects with CAA. Measures of inflammation will be compared to that of matched controls via paired statistical tests (e.g. McNemar's test for categorical outcomes or the paired t-test for continuous outcomes). Non-parametric alternatives will be considered only if distributional assumptions are violated.

**Control Group:** Controls will be chosen from the >600 subjects with data in our web-based data repository in REDCap. Controls will be matched to study patients based on age, sex, Illness Day at diagnosis, and baseline Z score.

**Analysis:** Each marker will be initially summarized descriptively and analyzed individually. Separate multivariable mixed effects regression modeling for clustered data (to account for the case-control paired nature of samples) will be used to characterize the markers of anakinra-treated subjects versus matched controls to adjust for any known confounders and additional time points (baseline, 48 hours, 2 weeks, and 6 weeks). In addition, any covariate at the individual level that is simultaneously unbalanced and associated with the outcome will be included in the model. Covariates of interest include demographic variables (e.g., ethnicity, Illness Day at diagnosis, response to IVIG therapy). Permutation tests may be implemented to verify that valid p-values will be obtained even if model assumptions are not correct. Note that the mixed model seamlessly accommodates different times of measurement (e.g. 2-week and 6-week time points) as well as missed measurements and data from subjects who are lost to follow-up. A corresponding Generalized Estimating Equations (GEE) model will be used as the sensitivity analysis method. An analogous secondary model including all subjects in this study will also be considered to examine the dose versus activity relationship. In this model, dosage will be included as a covariate to examine any dosage trend in activity.

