The above approach will be repeated for the other markers. That is, multi-level mixed effects regression models analogous to the above methodology will be applied for other markers: Levels of high sensitivity (hs) CRP, alpha-1 antitrypsin, TNFaR1 and R2, IFNg, IL-1 RAP, IL-1R1 and R2, MMP9, caspase-1, IL-6R, IL-18RAP, IL-12, IL-2, TGFb and IL-10.

Measures of transcript abundance will also be analyzed via microarray analysis. Data will be preprocessed first and then microarray analysis procedures will be used to measure abundance. The R software (version 3.0.2) and Bioconductor package in R will be used for the analysis. For coronary outcomes as assessed by echocardiography, we will compare the delta Z scores (baseline minus 2weeks and 6-weeks) between anakinra subjects and matched controls. A GEE model will be used as the sensitivity analysis method. Since this is a safety and early efficacy study, no adjustments for multiple comparisons will be made for biomarker analyses. P-values less than 0.05 will be considered statistically significant. All statistical analyses will be performed in R version 3.2.0 (www.rproject.org/). Similarly, analyses will be repeated on all subjects to characterize any dose-activity relationship, adjusting for dosage as a covariate in the model.

To determine the "best" or "set of best" markers that have the greatest improvement from baseline in anakinra-treated patients, ROC and AUROC analysis will be considered. In the event that there is

high multi-collinearity amongst the markers, we will adopt the "glmpath" approach, which is based on Least Angle Regression (LARS) methods to select the best biomarkers (Park 2007).

Missing data assumptions: The proposed mixed-effects regression model is consistent under the assumption that the outcome data are "missing at random" (MAR), that is, mixed models with a random effect assume only that the probability that an outcome is missing depends on observed outcomes. GEE models, which are proposed as a sensitivity analysis, assume that the outcome data are "missing completely at random", that is, that the probability that an outcome is missing does not depend on any previous, present or succeeding value of the outcome. This will enable us to assess the impact of the missing data mechanism on statistical inferences drawn from these models.

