Measures of transcript abundance will also be analyzed via RNAseq. The R software (version 3.0.2) and Bioconductor package in R will be used for the analysis. For coronary outcomes as assessed by echocardiography, we will compare the delta Z scores (baseline minus 2-weeks and 6-weeks) between anakinra subjects and matched controls. A GEE model will be used as the sensitivity analysis method. Since this is a pilot study, no adjustments for multiple comparisons will be made for biomarker analyses. P-values less than 0.05 will be considered statistically significant. All statistical analyses will be performed in R version 3.2.0 (www.r-project.org/).

Missing data assumptions: The proposed mixed-effects regression model is consistent under the assumption that the outcome data are "missing at random" (MAR), that is, mixed models with a random effect assume only that the probability that an outcome is missing depends on observed outcomes. GEE models, which are proposed as a sensitivity analysis, assume that the outcome data are "missing completely at random", that is, that the probability that an outcome is missing does not

depend on any previous, present or succeeding value of the outcome. This will enable us to assess the impact of the missing data mechanism on statistical inferences drawn from these models.

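### The coronary delta-Z comparison relies on matching alone to balance baseline Z, with no Z tolerance and no prespecified baseline-Z covariate

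*Combined protocol and SAP*

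**What the plan says.** The coronary sentence in 19B1 reads "we will compare the delta Z scores (baseline minus 2weeks and 6-weeks) between anakinra subjects and matched controls". For the pilot, 19B2 has "we will compare the delta Z scores (baseline minus 2-weeks and 6-weeks", again against matched controls. Neither sentence names a test or a covariate. The only addition in 19B1 is "A GEE model will be used as the sensitivity analysis method", also without covariates, and 19B2 says the same.

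Baseline Z is dealt with through the choice of controls, which is described in several ways:

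- 19B1 (and 19B2 likewise): "Controls will be matched to study patients based on age, sex, Illness Day at diagnosis, and baseline Z score".
- 18A: matching "by age (± 2 yrs. with lower limit of 2 yrs.), sex, and coronary artery Z-score". Age has a tolerance; Z has none.
- 9A, Specific Aim 2, which covers the echocardiographic comparison: controls "matched for age, sex, illness day at diagnosis, and coronary artery status on initial echo".
- 18B (pilot): matching on baseline coronary damage by echocardiogram, without naming a Z score.

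Every subject enters "with LAD or RCA z-score ≥ 2.5" (11B1; 11B2 has the same criterion). For the marker models, 19B1 and 19B2 provide for adjustment for known confounders and add that "any covariate at the individual level that is simultaneously unbalanced and associated with the outcome will be included in the model".

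**The concern.** A change score handles baseline differences correctly only if follow-up Z moves one for one with baseline Z. If the slope is below 1, subjects who start higher fall further whatever treatment they receive. Whichever group starts higher then shows the larger delta Z. Matching removes the problem to the extent that it equalises baseline Z. With no tolerance, and with matching wording that ranges from a Z value to a coronary status, the plan does not fix how close that will be.

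The stakes are moderate. Safety is the primary outcome in both studies (7F), and coronary Z is secondary (7G). But 7A states the goal as preventing or attenuating coronary damage, 8A1 expects the activity assessments to inform Phase III endpoints, and 19B applies p < 0.05 throughout. With about 18 treated subjects, or 10 in the pilot, chance will not reliably even out a mismatch.

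**Working it through.** **The plan's own figure.** The documents give no power or precision figure for delta Z, and 15B says the pilot is not powered for echocardiographic differences. The nearest figure is the 80% power in 15A, for transcript change scores in 18 matched pairs (two-sided paired t-test, alpha 0.05). The standardised differences are 2.2/3.2 = 0.6875 and 5.6/8 = 0.70. The noncentral t gives 78.5% and 79.9%, so the figure reproduces. It confirms that the plan thinks in paired change scores, but says nothing about Z.

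**Inputs for the bias.** From the documents: delta Z = baseline minus follow-up (19B1), 18 treated subjects and 18 matched controls (15A), entry at Z of 2.5 or more (11B). Not in the documents, and therefore assumed over a range: the slope b of follow-up Z on baseline Z, the residual SD, and the baseline difference between groups.

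**Bias formula.** Suppose there is no drug effect and both groups follow the same line, follow-up = a + b × baseline + error. The expected difference in delta Z is then

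bias = (mean baseline of treated − mean baseline of controls) × (1 − b).

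| Imbalance | b = 0.9 | b = 0.8 | b = 0.7 | b = 0.5 |
|---|---|---|---|---|
| 0 | 0 | 0 | 0 | 0 |
| 0.5 Z | 0.5 × 0.1 = 0.05 | 0.5 × 0.2 = 0.10 | 0.5 × 0.3 = 0.15 | 0.5 × 0.5 = 0.25 |
| 1.0 Z | 0.10 | 0.20 | 0.30 | 0.50 |

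A positive value favours study drug and arises when treated subjects start higher. If they start lower, the sign reverses.

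**How much imbalance matching could leave.** This was simulated with 18 pairs, no drug effect, residual SD 1, b = 0.5, and treated subjects about 1 Z above the control pool on average (all assumed):

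| Z matching | Mean imbalance | Bias, raw delta Z | Type I error, raw | Bias, baseline-adjusted | Type I error, adjusted |
|---|---|---|---|---|---|
| Exact | 0.000 | 0.005 | 5.1% | not fitted | not fitted |
| ± 0.5 Z | 0.026 | 0.010 | 4.4% | −0.003 | 4.6% |
| ± 1 Z | 0.098 | 0.042 | 5.2% | −0.007 | 5.2% |
| ± 2 Z | 0.293 | 0.152 | 7.0% | 0.003 | 5.4% |
| Only Z ≥ 2.5 | 1.024 | 0.518 | 16.7% | 0.011 | 5.3% |

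The formula agrees: 1.024 × 0.5 = 0.512 and 0.293 × 0.5 = 0.147. With matching only on Z ≥ 2.5, the bias is 0.298 at b = 0.7 (type I error 10.7%) and 0.102 at b = 0.9 (5.8%). If treated subjects and pool share one baseline distribution, the raw bias is 0.033 Z or less and type I error stays near 5% in every case.

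**Precision.** With matching within ± 1 Z and b = 0.5, the empirical SE is 0.335 to 0.338 for raw change and 0.342 to 0.347 after adjustment. Adjustment gains nothing here and costs slightly.

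**Which row does the plan specify?** The 19B wording points to matching on a Z value, but without a distance. The Specific Aim 2 wording could be met by a category. Section 11G defines a coronary aneurysm as Z of 2.5 or larger in the RCA or LAD, which every enrolled subject meets on entry, so status matching could reduce to the last row. Nothing in the documents settles between these readings.

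**The case against.** The strongest reply is that matching already does the work. Controls matched on baseline Z regress to the mean as treated subjects do, so a high entry threshold affects both groups alike. A reader might infer from the 2.5 threshold that delta Z is biased as such. The documents do not support that: only residual mismatch matters, and they permit it without showing that it exists or in which direction. This stands.

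Second, the rule for unbalanced prognostic covariates, or the adjustment for known confounders, might bring baseline Z in. It might, but both are written for the marker models, and the covariates listed as examples do not include baseline Z. 19B1 extends the approach to a named list of markers, while coronary Z has its own sentence. The rule also waits on observed imbalance, so it is not a prespecified adjustment.

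Third, baseline adjustment of non-randomised groups is open to dispute when they come from populations with different baselines. The adjusted columns above look good partly because the simulation gives both groups the same regression line. But matching on baseline Z makes the same assumption. Adding the covariate completes the conditioning that the plan has already chosen.

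Fourth, a reader might claim a variance gain of 10 to 35% from (1 + ρ)/2 at correlations of 0.8 to 0.3. That formula is for unmatched groups, and the gain vanishes with close matching. It should not be claimed here.

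**Conclusion.** The point holds as a gap in specification with a conditional bias. The coronary comparison depends on matching alone for balance in baseline Z, and the closeness of that matching is undefined. For an assumed 0.5 Z imbalance the bias is 0.05 to 0.25 Z at slopes of 0.9 to 0.5. In the simulated case at slope 0.5 it is about 0.01 to 0.04 Z when controls lie within 0.5 to 1 Z, and reaches 0.52 Z only if matching stops at Z ≥ 2.5 and treated subjects are about 1 Z sicker than the pool. Slope, residual SD, imbalance and its direction are all assumptions; the documents supply none of them.

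The case for change is protection against bias, not precision. It concerns a secondary outcome and leaves the primary safety assessment untouched. A reader might also want baseline adjustment for the inflammatory markers. That does not follow: controls are not matched on baseline markers, and 19B already models baseline as one of the marker time points.

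**What to change.** In 19B1 and 19B2, make the coronary analysis a model of 2- and 6-week Z with baseline Z as a prespecified covariate and matched set as a random effect. The random effect serves whether the ratio is the 1:1 of 15A or the 1:2 of 18A. Keep delta Z as a descriptive summary. Leave the marker models as they are.

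Replace the differing descriptions in 9A, 18A, 18B and 19B with one matching definition that states the Z tolerance and says which vessel and which echocardiogram supply the baseline Z. Report the achieved baseline-Z difference between groups.

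The cost is one degree of freedom for the baseline slope and, if matching proves tight, a slightly larger standard error (0.347 against 0.338 in the ± 1 Z example with sicker cases). The baseline echocardiogram is already collected. A tight tolerance may leave fewer eligible controls, so it should be set against the repository before controls are selected.

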## 7G. Secondary Outcomes

#### 7G1. Secondary Outcomes for Phase I/IIa anakinra study

- 1. Pharmacokinetics of anakinra
- 2. Immune-monitoring pre-and post-therapy
  - a. Enumeration of myeloid dendritic cell populations
  - b. Enumeration of activated CD4+ and CD8+ DR+ T cells, enumeration regulatory T cells
- 3. Measures of inflammation pre-and post-therapy
  - a. Transcript abundance changes over time by RNAseq
  - b. Levels of high sensitivity (hs) C-reactive P (CRP), alpha-1 antitrypsin, TNFaR1 and R2, IFNg, IL-1 RAP, IL-1R1 and R2, MMP9, caspase-1, IL-6R, IL-18RAP, IL-12, IL-2, TGFb and IL-10
- 4. Echocardiographic assessment of coronary artery internal diameters expressed as Z scores pre-and post-therapy

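### Section 19B1 sets no multiplicity adjustment and p<0.05 for a Phase I/IIa transcript analysis that is not limited to named genes; if run array-wide, this could yield several hundred or more false calls per contrast

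*Combined protocol and SAP*

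**What the plan says.** Transcript change is a secondary outcome of the Phase I/IIa study. Section 7G1 lists it as "Transcript abundance changes over time by RNAseq". Section 18A says "Transcript abundance will be measured in whole blood by microarray" and adds that transcript results will be compared with matched database controls. The two sections differ on platform, and neither gives a gene list.

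Section 19B1 follows the microarray version: "Measures of transcript abundance will also be analyzed via microarray analysis". The method is described only as "Data will be preprocessed first and then microarray analysis procedures will be used to measure abundance", with R and Bioconductor as software. No package or adjustment option is named. Later in the same paragraph come "Since this is a safety and early efficacy study, no adjustments for multiple comparisons will be made for biomarker analyses" and "P-values less than 0.05 will be considered statistically significant". Nothing exempts transcripts.

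Section 15A gives the only transcript-level power statement. It covers several IL-1 family transcripts, at two-sided alpha 0.05 with 18 case-control pairs.

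The combination study is written differently. Section 7G2 confines its RNAseq to the analytes listed there, and section 18B names the assays for those analytes.

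**The concern.** Leaving a short, pre-named list of markers unadjusted in an early study is a defensible choice. The 16 markers listed in 19B1 give 16 × 0.05 = 0.8 expected false positives per time point. The same rule applied to a whole array or transcriptome is different in kind, because the expected number of false calls grows in proportion to the number of transcripts.

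At stake is how the list of changed transcripts is read. Section 8A1 says the activity assessments will help determine end-points for a future Phase III study, and transcript change is one of them. If the list comes from array-wide testing at unadjusted 0.05, a reader cannot tell from the p-values how much of it is chance.

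**Working it through.** **Inputs from the documents.** Per-test level 0.05 and no adjustment (19B1). At least 18 cases and 18 matched controls, two-sided paired t-test, 80% power (15A). IL-1RAP: difference 2.2, SD 3.2. IL-1R1: difference 5.6, SD 8 (both 15A).

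**Assumed, because the documents do not give it.** The number of transcripts tested, G: 10,000 to 25,000 as the main range.

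**1. The plan's own power figure.** Take the stated pooled SD as the SD of the paired differences. The effect sizes are 2.2/3.2 = 0.6875 and 5.6/8 = 0.70. Exact noncentral-t power with 18 pairs (17 degrees of freedom, two-sided 0.05) is 78.5% and 79.9%. The stated 80% is reproduced to within 2 points. It is power for a single transcript at 0.05 and makes no allowance for many.

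**2. Expected false calls if anakinra changes no transcript.** Expected number = 0.05 × G. Correlation between transcripts does not alter this mean.

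| G (assumed) | Expected false calls per contrast |
|---|---|
| 2,000 | 100 |
| 4,000 | 200 |
| 10,000 | 500 |
| 20,000 | 1,000 |
| 25,000 | 1,250 |
| 50,000 | 2,500 |

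**3. Spread around that mean.** Paired t-tests with 18 pairs were simulated under no effect, with transcripts in 50 blocks. For G = 20,000, the central 95% of runs gave 939 to 1,058 false calls with no correlation and 636 to 1,523 with within-block correlation 0.5. For G = 10,000 at correlation 0.5, the range was 322 to 712. The smallest count in any run at G of 10,000 or more was 285.

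**4. Share of calls that are false when some transcripts do change.** Let a fraction π change with effect size 0.70, so that power is 0.799. Then

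false share = 0.05(1 − π) / [0.05(1 − π) + 0.799π], which does not depend on G.

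- π = 1%: 0.0495 / (0.0495 + 0.0080) = 86%
- π = 5%: 0.0475 / (0.0475 + 0.0400) = 54%
- π = 10%: 0.0450 / (0.0450 + 0.0799) = 36%

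**5. The same tests with Benjamini-Hochberg at 5%.** Under no effect, for G from 10,000 to 47,000 (100 to 200 runs per setting), any transcript was called in 2% to 8% of runs, in line with the nominal 5%. The mean was 0.02 to 0.09 false calls per analysis, against about 500 to 2,350 unadjusted.

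**6. The combination study.** Section 7G2 lists nine analytes: 9 × 0.05 = 0.45 expected false calls per time point.

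**The case against.** The strongest reply is that 19B1 is ambiguous. The term biomarker is not defined. The no-adjustment sentence directly follows the echocardiography text, not the microarray text. No per-transcript test or gene list is spelled out, and the only quantified transcript hypothesis, in 15A, concerns a few IL-1 family transcripts. On this view the plan is merely underspecified.

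Part of this stands: the wording could be narrower than it looks. But 15A itself powers the study on transcript levels at 0.05, so transcripts are among the tested markers, and 18A says transcript results will be compared with controls. Section 7G2 shows that a restriction is written down when one is intended. Nor can an adjustment be presumed from the software. None is named, the written rule is not to adjust, and a figure legend in 8A1 describes its probe p-values as uncorrected.

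A reader might also infer four stronger things, which the documents do not support:

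- That hundreds of false calls are certain. The count depends on an assumed G and on no true effect. With fewer than about 2,000 to 4,000 transcripts it falls to 200 or below.
- That the count triples over 48 hours, 2 weeks and 6 weeks. Separate array-wide contrasts at each time are not specified. 19B1 handles time within a mixed model for each marker, and 11E1 collects 6-week samples only from subjects still on drug.
- That the list would be mostly noise whatever the drug does. At 10% truly changed, the false share is 36%.
- That section 19B2 has the same fault, because it says "Since this is a pilot study, no adjustments for multiple comparisons will be made for biomarker analyses". Sections 7G2 and 18B limit that study to listed analytes.

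The marker-selection tools in 19B1 are ROC analysis and a penalised regression path, and no section feeds a p<0.05 transcript list directly into the choice of end-points.

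**Conclusion.** The point holds for the transcript analysis in 19B1. As written, the rule allows array-wide testing at unadjusted 0.05. Under no effect, that gives about 500 to 1,250 false calls per contrast for an assumed 10,000 to 25,000 transcripts. With 1% to 5% of transcripts truly changed at an effect size of 0.70 and 18 pairs, roughly 86% to 54% of calls would be false. These figures rest on the assumed transcript count, on the plain reading that the no-adjustment rule covers transcripts, and on taking the pooled SD in 15A as the SD of paired differences. The consequence is confined to a secondary, early-activity result. The primary safety outcome does not depend on it, and the absence of adjustment is openly declared. It should be changed, but it does not threaten the study.

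**What to change.** Change 19B1 only. Add a sentence to this effect: for any array- or sequencing-wide transcript analysis, the false discovery rate will be controlled (Benjamini-Hochberg, for example at 5%) over all transcripts within each contrast tested, and a transcript will be called changed only on the adjusted value. Name the IL-1 family transcripts in advance as a separate small set. Keep them and the 16 listed markers at unadjusted 0.05, which leaves the power statement in 15A as it is. The wording covers either platform, so it works whether microarray or RNAseq is used.

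The cost is one or two sentences, with no change to patients, samples or the safety analysis. The downside is that fewer transcripts will be declared changed, and with 18 pairs some true changes outside the named set will be missed.
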